7.1.1 Baseline

Parent-study baseline is defined as the last value recorded for any given parameter prior to first study medication injection in the OA-11 (parent) study.

OA-07-study baseline is defined as the last value recorded for any given parameter prior to first study medication injection in the OA-07 study and on or after Week 52 of the parent-study.

OA-07-study visit 3E baseline is defined as the value recorded for any given parameter in the OA-07 study Visit 3E.

7.1.2 Analysis of Covariance

Analysis of Covariance (ANCOVA) will be used for continuous efficacy outcome measures to test the following hypotheses:

$$H_0: (\beta_1 - \beta_0) = 0$$

$$H_A: (\beta_1 - \beta_0) \neq 0$$

In the statement above, β is the least squares estimate in the change in the continuous efficacy outcome from baseline, where β_0 is the estimate for placebo and β_1 is the estimate for the active treatment group. The models will be adjusted for baseline value of the outcome.

7.1.3 Data Handling for Patients Who Withdrew from the Study

If a subject discontinued the study, early termination assessments were performed according to the protocol. If these assessments occurred during a scheduled visit, they will be associated with that visit for the purposes of FAS analysis.

7.1.4 Imputation of Missing Data

Sensitivity analysis will be performed using multiple imputation (MI) for the primary and secondary endpoints. Missing data will be imputed based upon the observed data for each outcome under the MAR assumption following the paradigm first developed by Rubin (Shafer, 1999). The imputation will adjust for the outcome's baseline data in a regression model with data imputed independently for each timepoint. A total of 10 imputation datasets will be created and analyzed based upon accepted convention (Shafer, 1999). Error estimates of the multiple imputation itself, as well as an overall summary of the efficacy analysis, will be averaged across the 10 imputed datasets based upon Rubin's paradigm.

Specifically, let Q denote the imputed mean of an efficacy outcome Y subject to missing data at a given timepoint, where the estimate of that mean for any i^{th} imputation would be defined as function of both observed and missing such that

$$\widehat{Q^{(i)}} = E\left(Q^{(i)} | Y_{observed}, Y_{missing}^{(i)}, Y_{Baseline}, I(Group)\right), i = 1, \dots, 10.$$

After all 10 datasets have been imputed, the overall estimate of Q is a simple average defined as

$$\bar{Q} = \frac{\sum_{i=1}^{10} \widehat{Q}^{(i)}}{10}.$$

For this analysis using 10 imputed datasets, the variance of \bar{Q} is defined as

$$Var(\bar{Q}) = 1.1B + \bar{U}$$

where B is the between imputation variance and U is the within imputation variance:

$$B = \frac{1}{9} \sum_{i=1}^{10} \left(\widehat{Q}^{(i)} - \bar{Q} \right)^2;$$

$$\bar{U} = \frac{\sum_{i=1}^{10} U^{(i)}}{10}.$$

PROC MI in SAS® will be used to impute missing data assuming missingness is monotone in pattern. If a subject is missing a baseline record causing non-monotone missingness, all non-missing post-baseline records will temporarily be set to missing as well. After the 10 imputation datasets are created, the non-missing post-baseline will be merged back in, thus creating complete datasets where only the originally missing records were imputed. Imputations will be performed with a seed of 469007.

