7.3.3 TERMINATION VISIT

The following procedures and assessments should be performed on subjects who withdraw or are discontinued from the study.

- Pain NRS assessment
- WOMAC questionnaire
- PASS assessment
- SF-36
- Collection of AE and concomitant procedures/therapies/medication data
- Assessment of NSAID/acetaminophen usage

Protocol SM04690-OA-07
Biosplice Therapeutics, Inc.

AM02V00
04 May 2021

- Review of medical history
- Physical examination
- Knee examination
- Weight measurement
- Vital sign measurements (pulse rate and blood pressure)
- Venipuncture and collection of samples for clinical laboratory tests
- Radiograph – bilateral in weight-bearing fixed flexion position, PA view X-ray (if not completed within 12 weeks before the Termination Visit)

Note: Subjects who withdraw from the study after having a partial or total knee replacement are not required to complete the pain NRS assessment, WOMAC questionnaire, PASS assessment, SF-36, or radiograph.

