10.4.3 ANALYSIS OF EFFICACY ENDPOINT(S)

Change over time through Visit 3E in mJSW, pain NRS, WOMAC Pain, WOMAC Function, and WOMAC Total will be characterized using mixed-effects models for repeated measures (MMRM). The models will estimate change from parent-study baseline with treatment, visit, treatment \times visit interaction, and parent-study baseline value as covariates. Unadjusted 95% confidence intervals and *P* values will be reported. The potential confounding effect of change in NSAID/acetaminophen usage on the treatment effect will be considered for sensitivity analysis.

ANCOVA will be used to analyze the change in SF-36 domain scores and summary component scores through Visit 3E. Change will be assessed from parent-study baseline between the active and placebo treatment groups. The models will be adjusted for parent-study baseline. Unadjusted 95% confidence intervals and *P* values will be reported.

PASS will be analyzed using logistic regression. Logistic regression will also be used to compare the proportion of Outcome Measures in Rheumatology Clinical Trials (OMERACT)-Osteoarthritis Research Society International (OARSI) responders and “strict” responders ([Pham et al. 2003](#)) between treatment groups through Visit 3E, as well as proportion of subjects achieving a 20%, 50%, and 70% improvement.

Maintenance of LOR’s effects on pain and function of the target knee will be characterized by summarizing likelihood of response in pain NRS, WOMAC Pain, and WOMAC Function in the current study for those subjects that had a response in the parent study. Response will be characterized as a 20%, 50%, and 70% improvement.

After all subjects have received LOR at Visit 3E, all further efficacy analyses will be descriptive in nature.

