6.4 Modified Full Analysis Set

The Modified Full Analysis Set (mFAS) includes all FAS subjects who completed Visit 3E (Week 48).

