9.4 Primary Efficacy Analysis

9.4.1 Main Analysis

Parent-study baseline-adjusted ANCOVA will be used to assess the change in mJSW at Visit 3E (Week 48) in the FAS.

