13. CHANGES TO PLANNED ANALYSIS

Change	Protocol Section	Rationale
Per protocol, efficacy endpoints were simply listed. In the SAP, we clearly define efficacy endpoints into categories of primary, secondary, and other. Additionally, an mFAS for completers of Visit 3E (Week 48) was defined as well as a CAS for subjects with an available mJSW at Visit 6E (Week 100).	3.2 and 6.4	Based on study team decision and clinicaltrials.gov reporting.
Per protocol, mixed-effects models for repeated measures (MMRM) would be used. In SAP we describe the use of ANCOVA. Additionally, the protocol mentioned ‘potential confounding effect of change in NSAID/acetaminophen usage on the treatment effect’ will not be considered as a sensitivity analysis.	9	More appropriate model and elimination of a sensitivity analysis given the spacing of the visits/assessment collection in the OA-07 study as compared to the OA-11 study.
Per protocol, “After all subjects have received LOR at Visit 3E, all further efficacy analyses will be descriptive in nature.” See section 9.4.4 regarding the efficacy analysis pertaining to the “Open-label” portion of the study.	9	Based on study team decision.
Per protocol, “Outcome Measures in Rheumatology Clinical Trials (OMERACT)-Osteoarthritis Research Society International (OARSI) responders and ‘strict’ responders” would be estimated. Only “strict” responders will be estimated.	10.4.3	One of the components comprising OMERACT-OARSI response, Patient Global Assessment of Disease Activity, was not collected.

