15.2 Appendix 2 – Estimands

	Estimator	Variable	Population	Intercurrent events	Population level summary
Primary	Main	Change from parent-study baseline in mJSW at Visit 3E (Week 48)	FAS	Prohibited medications and NSAID/acetaminophen use: treatment policy strategy; analysis will be conducted regardless of use of prohibited medications or NSAID/acetaminophen use.	Difference in the change from parent-study baseline between LOR and placebo using parent-study baseline-adjusted ANCOVA with available data.
	Sensitivity 1	Change from parent-study baseline in mJSW at Visit 3E (Week 48)	FAS	Prohibited medications and NSAID/acetaminophen use: treatment policy strategy; analysis will be conducted regardless of use of prohibited medications or NSAID/acetaminophen use.	Difference in the change from parent-study baseline between LOR and placebo using parent-study baseline-adjusted ANCOVA with missing data imputed using the MI method.
	Sensitivity 2	Change from parent-study baseline in mJSW at Visit 3E (Week 48)	mFAS	Prohibited medications and NSAID/acetaminophen use: treatment policy strategy; analysis will be conducted regardless of use of prohibited medications or NSAID/acetaminophen use.	Difference in the change from parent-study baseline between LOR and placebo using parent-study baseline-adjusted ANCOVA with available data.
	Sensitivity 3	Change from parent-study baseline in mJSW at Visit 3E (Week 48)	PPAS	1) Prohibited medications: principal stratum strategy; subjects who used prohibited medications will be excluded from this analysis. 2) NSAID/acetaminophen: treatment policy strategy; analysis will be conducted regardless of NSAID/acetaminophen use.	Difference in the change from parent-study baseline between LOR and placebo using parent-study baseline-adjusted ANCOVA.
Estimand is repeated using the OA-07-study baseline as Secondary					

Secondary	Estimator	Variable	Population	Other intercurrent events	Population level summary
	Main	Change from parent-study baseline in Pain NRS at Visit 3E (Week 48)	FAS	Prohibited medications and NSAID/acetaminophen use: treatment policy strategy; analysis will be conducted regardless of use of prohibited medications or NSAID/acetaminophen use.	Difference in the change from parent-study baseline between LOR and placebo using parent-study baseline-adjusted ANCOVA with available data.

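### The primary endpoint's multiple imputation uses the same covariates as the primary ANCOVA, so it cannot reveal bias from dropout that follows Visit 2E

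*SAP*

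**What the plan says.** **Main analysis.** SAP 9.4.1: "Parent-study baseline-adjusted ANCOVA will be used to assess the change in mJSW at Visit 3E (Week 48) in the FAS". SAP Appendix 2 defines the summary as the difference "between LOR and placebo using parent-study baseline-adjusted ANCOVA with available data". For early-termination assessments SAP 7.1.3 adds: "If these assessments occurred during a scheduled visit, they will be associated with that visit for the purposes of FAS analysis". A subject with no mJSW value at Visit 3E, scheduled or mapped in this way, therefore contributes nothing to the primary estimate.

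**Imputation check.** SAP 7.1.4 assumes missing-at-random (MAR), creates ten datasets, and adjusts for the outcome's "baseline data in a regression model with data imputed independently for each timepoint". The formula below that sentence also conditions on treatment group; the sentence does not mention it. The only cause of non-monotone missingness the section deals with is a missing baseline record. That fits a model in which baseline is the only other measurement used.

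**Other checks.** SAP 9.4.2 repeats the analysis in three sets. The mFAS "includes all FAS subjects who completed Visit 3E (Week 48"). The completers set (CAS) needs an mJSW result at Week 100. The per-protocol set (PPAS) needs completion of Visit 6E and no relevant major deviation.

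**What was planned before.** Protocol 10.4.3 specified an MMRM through Visit 3E. SAP 13 declares the change: "Per protocol, mixed-effects models for repeated measures (MMRM) would be used. In SAP we describe the use of ANCOVA". The reason it gives is the spacing of the visits. Radiographs are taken at Visit 2E (Protocol 7.3.2) and at Week 52 of the parent study (Protocol Figure 1, footnote).

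**Knee replacement.** Protocol 7.3.3: "Subjects who withdraw from the study after having a partial or total knee replacement are not required to complete the pain NRS assessment"; the radiograph is on the same list. The intercurrent events named in SAP Appendix 2 are prohibited medication and NSAID/acetaminophen use only.

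**The concern.** A missing-data sensitivity analysis is informative only if it uses information, or makes an assumption, that the main analysis does not. Here the imputation model and the analysis model share their predictors. Agreement between them is built in, and a reader of the report could take it for reassurance.

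Suppose subjects leave between Visits 2E and 3E because of what has happened by Visit 2E, and do so differently by arm. The primary estimate is then biased, and the imputation and mFAS results carry the same bias. CAS and PPAS condition on still later retention, so they do not test the assumption either. No delta-adjusted, tipping-point or reference-based analysis is planned. Discontinuation and target-knee replacement, an event plausibly linked to structural worsening, have no stated strategy.

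**Working it through.** **1. Inputs.** From the documents: two mJSW visits in this study up to Week 48 (2E and 3E); ANCOVA on treatment and baseline; ten imputations; up to approximately 500 subjects, set on practical grounds (SAP 5). Not given, so assumed: 1:1 allocation, N = 500, dropout d between 2E and 3E of 10–30% in each arm, and correlation ρ of 0.5–0.8 between the 2E and 3E changes. Results are in residual SD units of the change.

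**2. The plan's own figures.** With m = 10, the between-imputation factor is 1 + 1/10 = 1.1 and the divisor is 10 − 1 = 9. Both match SAP 7.1.4. There is no power calculation to reproduce.

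**3. Why the imputation repeats the ANCOVA.** Let X hold intercept, treatment and baseline, with rows o (observed at 3E) and m (missing). The ANCOVA estimate b satisfies X_o′y_o = X_o′X_o b. Imputed values average X_m b. Refitting on the completed data gives, on average,

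(X_o′X_o + X_m′X_m)⁻¹ (X_o′X_o b + X_m′X_m b) = b.

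This holds for any dropout pattern, SD or correlation.

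**4. Size when dropout differs by arm.** Simulation of 400 trials per row. The true difference is 0. LOR subjects with a poor Visit 2E change are more likely to leave; placebo dropout is random at the same rate. Monte Carlo error is about 0.1/√400 = 0.005.

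| ρ | d | ANCOVA | SAP imputation | Imputation + 2E | MMRM | 2E difference, FAS | 2E difference, mFAS |
|---|---|---|---|---|---|---|---|
| 0.5 | 10% | 0.045 | 0.045 | 0.000 | 0.001 | 0.001 | 0.088 |
| 0.5 | 20% | 0.089 | 0.091 | 0.001 | 0.002 | −0.008 | 0.165 |
| 0.5 | 30% | 0.135 | 0.135 | 0.005 | 0.006 | 0.002 | 0.260 |
| 0.8 | 10% | 0.072 | 0.072 | −0.001 | −0.001 | 0.000 | 0.090 |
| 0.8 | 20% | 0.141 | 0.142 | 0.000 | 0.001 | 0.000 | 0.175 |
| 0.8 | 30% | 0.199 | 0.199 | −0.004 | −0.005 | −0.004 | 0.252 |

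Hand check: the bias should be about ρ × (mFAS − FAS difference at 2E). First row: 0.5 × (0.088 − 0.001) = 0.044, against 0.045. Last row: 0.8 × (0.252 + 0.004) = 0.205, against 0.199.

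**5. Other mechanisms.** Across all 24 scenarios (four mechanisms, two values of ρ, three dropout rates) the SAP imputation differs from the ANCOVA by at most 0.002.
- Dropout follows Visit 2E alike in both arms: every method is within 0.005 of zero.
- LOR dropout follows the unseen part of Visit 3E: ANCOVA, MMRM and imputation with 2E are equally biased, by 0.05 to 0.22. The 2E comparison of FAS with mFAS does not move.

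**6. If treatment group is left out,** as the sentence in SAP 7.1.4 could be read, the estimate shrinks to about true effect × (1 − d) even under completely random dropout. A true 0.25 becomes 0.25 × 0.9 = 0.225, 0.25 × 0.8 = 0.200 and 0.25 × 0.7 = 0.175. The simulated means are 0.221–0.225, 0.197 and 0.173–0.176.

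**7. Precision.** Var(MMRM)/Var(ANCOVA) = 1 − ρ²d. This runs from 1 − 0.25 × 0.1 = 0.975 to 1 − 0.64 × 0.3 = 0.808. At an assumed 0.25 SD effect, power rises from 75.5% to 76.6–78.3% at 10% dropout, and from 64.7% to 68.1–73.9% at 30%.

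**The case against.** The case for the plan has force. ANCOVA is valid if missingness depends only on baseline and arm. The change from MMRM is declared with a reason. MMRM is itself a MAR analysis and does no better when dropout follows the unseen Visit 3E value. The bias needs dropout that is both outcome-related and different by arm, and the documents give nothing to size it. The knee-replacement waiver covers only subjects who withdraw after surgery, and no event rate is given. All of this stands, and it limits the point to the sensitivity analyses.

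The visit-spacing rationale is weaker. With visit as a categorical effect and an unstructured covariance, equal spacing is not needed. The protocol, however, names no covariance structure.

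Four stronger readings are tempting, and the documents do not support them.
- **No planned analysis can detect dropout bias.** Visit 2E outcomes are planned in both FAS and mFAS (SAP 9.5.2, 9.6 and Appendix 2). The last two columns of the table show that this contrast reacts when dropout follows Visit 2E differently by arm. It is an indirect signal, not labelled as a dropout check, and it does not correct the primary estimate.
- **The protocol MMRM would have used parent-study follow-up.** Protocol 10.4.3 lists treatment, visit, their interaction and parent-study baseline. It does not make parent post-baseline visits outcomes. Visit 2E is the clear loss.
- **About half the effect disappears.** One assumed scenario does give this: 250 per arm, true difference 0.10 mm, 16% and 12% missing, placebo dropout following Visit 2E loss. ANCOVA and the SAP imputation both average 0.046 mm, and adding Visit 2E gives 0.0995 mm. If all the bias arises in placebo, its dropouts must average 0.054/0.16 = 0.34 mm worse than those who stay, or 0.054/0.12 = 0.45 mm at the lower rate. Nothing in the documents supports or excludes that.
- **An unblinded sponsor chose the weaker model for its result.** SAP 4.4 puts sponsor unblinding at parent-study lock, and Protocol 10.6.1 foresaw it. The documents do not date the model decision or suggest a motive.

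**Conclusion.** Should-fix. It is certain from the documents, by algebra, that the imputation described in SAP 7.1.4, with group included, returns essentially the primary estimate. The Visit 3E mFAS analysis adds almost nothing to it, and CAS and PPAS do not vary the missing-data assumption.

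Whether the primary estimate is biased, and in which direction, is not known. Under the assumed dropout and correlation, arm-differential dropout that follows Visit 2E gives about 0.05–0.20 SD; dropout acting alike in both arms gives about zero. A reader might infer that the ANCOVA must be replaced as the main analysis. The evidence does not go that far: the defect lies in the checks around it, and any MAR replacement would leave dropout on unseen values untested.

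**What to change.** 1. Keep the Visit 3E ANCOVA as the main analysis.
2. In SAP 7.1.4, impute sequentially within treatment group from baseline, parent Week 52 mJSW where available (for other outcomes, the latest parent-study value available) and Visit 2E. Name treatment group in the text as well as in the formula. State how a missing Visit 2E with an observed Visit 3E is handled, for example by fully conditional specification, because that pattern is not monotone.
3. Together with item 2, or in its place, report the protocol MMRM as a sensitivity analysis for the primary and secondary endpoints.
4. Since items 2 and 3 are still MAR analyses, add one delta-adjusted or reference-based imputation covering discontinuation and target-knee replacement. Name both as intercurrent events in Appendix 2 with a stated strategy. The choice of method is open; what matters is that it is written down before results are seen.
5. Describe mFAS at Visit 3E as a consistency check, not as a test of the missing-data assumption.

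Cost: SAP wording, modest programming and one or two extra tables. The plan already provides for collecting the Visit 2E and parent-study values, and subjects keep their parent-study numbers (Protocol 7.3.1).

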9.4.2 Sensitivity Analysis

Missing data will be imputed using the MI method as described in Section 7.1.4. The main primary analysis will also be repeated for subjects in the mFAS, CAS, and PPAS.

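### With only 10 imputations, the MI sensitivity P value carries avoidable Monte Carlo noise when the result is near 0.05; at least 100 would be better

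*SAP*

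**What the plan says.** SAP 7.1.4 defines the role of MI: "Sensitivity analysis will be performed using multiple imputation (MI) for the primary and secondary endpoints". It fixes the number of datasets ("A total of 10 imputation datasets will be created and analyzed based upon accepted convention") and the seed ("Imputations will be performed with a seed of 469007"). The text describes the imputation model this way: "The imputation will adjust for the outcome's baseline data in a regression model with data imputed independently for each timepoint". The displayed formula below it also conditions on treatment group. The pooled variance is written with the constants for ten datasets: 1.1 times the between-imputation variance B plus the mean within-imputation variance, with 1/9 as the divisor for B. No target is set for Monte Carlo error.

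The primary analysis does not impute. SAP 9.4.1 says: "Parent-study baseline-adjusted ANCOVA will be used to assess the change in mJSW at Visit 3E (Week 48) in the FAS", and Appendix 2 specifies available data for it. SAP 9.4.2 then adds the sensitivity analyses: "Missing data will be imputed using the MI method as described in Section 7.1.4", followed by "The main primary analysis will also be repeated for subjects in the mFAS, CAS, and PPAS". SAP 9.5.2 does the same for the secondary endpoints. Appendix 2 lists MI as Sensitivity 1.

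**The concern.** A convention about the number of imputations usually concerns the efficiency of the point estimate. Ten is often enough for that. It is less comfortable when a reader will compare two P values, because the MI result then includes a random component that would have been different under another seed.

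Here the comparison is especially exposed. With only baseline and group in the imputation model, MI is centred on the available-data ANCOVA. For a borderline result, a visible gap between the two P values would therefore be largely simulation noise, yet it would naturally be read as evidence for or against robustness to missing data. The same ten-dataset procedure serves the primary endpoint and all secondary endpoints, so there are many chances for such a gap.

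**Working it through.** **The plan's own constants.** Rubin's rules give a multiplier of 1 + 1/m on B and a divisor of m − 1. With m = 10 these are 1 + 1/10 = 1.1 and 9. Both match SAP 7.1.4.

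**Inputs**
- From the SAP: m = 10, regression imputation under missing at random, group included as in the displayed formula, and up to about 500 subjects (Section 5).
- Assumed: two-sided 0.05, since Section 7.1.2 is two-sided and Section 9.6.1 reports 95% intervals but no alpha is stated; 1:1 allocation; values missing completely at random; baseline–outcome correlation 0.5; missing fraction 5% to 30%, since none is given.

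**Hand check.** The Monte Carlo SD of the pooled difference is √(B/m). In units of its standard error this is about √(FMI/m), where FMI is the fraction of missing information, here close to the missing fraction. At m = 10:
- 5%: √(0.05/10) = 0.071
- 10%: √(0.10/10) = 0.100
- 20%: √(0.20/10) = 0.141
- 30%: √(0.30/10) = 0.173

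A main P of 0.04 is z = 2.054, only 2.054 − 1.960 = 0.094 from the 0.05 boundary. That is less than one noise SD at 10% missing. At 20%, 2.054 ± 1.96 × 0.141 runs from 1.777 to 2.331, which is P from 0.076 down to 0.020. This is somewhat too narrow, because B is itself estimated from ten values and the pooled standard error therefore also varies by seed.

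**Simulation.** For N = 300 and N = 500, one dataset was fixed per scenario and shifted so that the available-data ANCOVA gave exactly P = 0.04. It was then imputed repeatedly with baseline and group in the model and pooled by Rubin's rules with small-sample degrees of freedom (3,000 seeds at m = 10, 400 at m = 100).

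| Assumed missing | m = 10: P, central 95% of seeds | m = 10: seeds with P > 0.05 | m = 100: P, central 95% of seeds |
|---|---|---|---|
| 5% | 0.028–0.058 | 12–14% | 0.035–0.045 |
| 10% | 0.024–0.069 | 24–26% | 0.035–0.049 |
| 20% | 0.018–0.093 | 35–36% | 0.032–0.051 |
| 30% | 0.013–0.119 | 42–44% | 0.028–0.057 |

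Repeat runs move the range limits by a few thousandths and the shares by two or three percentage points. The simulated noise at m = 10 was 0.07, 0.10, 0.14 and 0.18 standard errors, in line with the hand check. The median MI P value was 0.040 to 0.045, which confirms that MI is centred on the main result.

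Starting instead from a main P of 0.05 (N = 500) gives the same picture. The range at m = 10 is 0.031–0.083 at 10% missing and 0.023–0.110 at 20%. At m = 100 these become 0.043–0.058 and 0.041–0.064.

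**The case against.** Much can be said for leaving this alone, and several stronger readings fail.

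- **The fixed seed is not a fault.** A reader might infer that one hard-coded seed is the defect. Naming the seed in advance makes the run exactly repeatable and prevents choosing a seed afterwards. The noise comes from m = 10.
- **The primary result does not depend on the seed.** SAP 9.4.1 and Appendix 2 use available data without imputation. The SAP has no rule that the MI P value must fall below 0.05, or that the primary finding otherwise counts as not robust.
- **MI is not the only sensitivity analysis.** The mFAS, CAS and PPAS repeats are also planned. They are subset analyses that do not impute or test the missing-at-random assumption, but they exist. The accurate statement is that MI is the only analysis that imputes.
- **The interval is not invalid.** The term 1.1B already allows for a finite number of imputations. Ten datasets cost precision and stability, not validity.
- **No single P value range can be stated as fact.** A spread of roughly 0.02 to 0.10 needs about 15% to 25% missing. At 5% the range is 0.028 to 0.058.
- **The affected band is narrow.** At a main P of 0.01 (z = 2.576) the distance to the boundary is 0.616, at least 0.616/0.18 = 3.4 noise SDs, so a seed would rarely change the side.

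It is also fair that a larger m does not answer whether the imputation model is adequate. With baseline and group only, a precise MI mostly returns the main analysis. All of this stands and limits the weight of the point. It does not make ten a better choice than one hundred.

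**Conclusion.** The point holds as a minor improvement. With m = 10 and a main P of 0.04, noise alone moves the MI P value across 0.05 for roughly one seed in eight at 5% missing, one in four at 10%, a little over one in three at 20% and more than two in five at 30%. These figures rest on the assumed missing rates, 1:1 allocation, values missing completely at random, and group being in the imputation model as the displayed formula shows. If group were left out, as the sentence in SAP 7.1.4 alone could be read, the estimate would shrink towards zero and the ranges would not apply; the text and formula should be reconciled. What is at stake is only how a borderline sensitivity result is read, not the primary conclusion.

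**What to change.** In SAP 7.1.4:
- set m to at least 100;
- keep seed 469007, so that no question of seed selection arises;
- write the constants as (1 + 1/m) and 1/(m − 1), which are 1.01 and 1/99 at m = 100;
- replace every other hard-coded ten: the index range, the summation limits, the divisors for the pooled estimate and the within-imputation variance, and the surrounding sentences;
- report the Monte Carlo error of the pooled difference, √(B/m), beside each MI result.

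The last item matters because m = 100 reduces the noise without removing it. At 30% missing and a main P of 0.04, about 10–12% of seeds would still give P above 0.05.

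Computing time is trivial. The real cost is procedural. The SAP was signed in November 2023, and SAP 4.4 says the sponsor was unblinded once the parent-study database was locked. The change should therefore be a documented SAP amendment, or a supplementary run reported beside the ten-dataset result.

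### The multiple-imputation rule for a missing baseline ignores the subject's own observed outcomes, which inflates the standard error of the MI sensitivity analyses when baseline and outcome are highly correlated

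*SAP*

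**What the plan says.** SAP 7.1.4 gives multiple imputation a supporting role: "Sensitivity analysis will be performed using multiple imputation (MI) for the primary and secondary endpoints". Appendix 2 lists it as Sensitivity 1. The stated basis is that "Missing data will be imputed based upon the observed data for each outcome under the MAR assumption", and the model is described thus: "The imputation will adjust for the outcome's baseline data in a regression model with data imputed independently for each timepoint". The software step assumes a monotone pattern: "PROC MI in SAS® will be used to impute missing data assuming missingness is monotone in pattern".

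A missing baseline with observed follow-up breaks that pattern. The SAP handles it by hiding the follow-up ("all non-missing post-baseline records will temporarily be set to missing as well"), imputing, and then restoring it: "the non-missing post-baseline will be merged back in, thus creating complete datasets". The baseline drawn in between is kept.

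SAP 7.1.2 adjusts every ANCOVA for the baseline value of the outcome. SAP 7.1.1 defines two main baselines. The second, used in seven hypotheses of SAP 9.2, must be recorded "prior to first study medication injection in the OA-07 study and on or after Week 52 of the parent-study".

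**The concern.** For the affected subjects, the most informative data on the missing baseline are their own later measurements, and these are set aside at the moment of imputation. The baseline is drawn from the group distribution at best, then placed beside a real outcome. To illustrate, a knee measured at 1.5 mm could be given a 4 mm baseline and so a 2.5 mm loss that never happened.

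The imputed baseline is used twice, in the change score and as the covariate. The relation between baseline and outcome, which ANCOVA relies on for precision, is destroyed for these subjects and diluted for the whole sample.

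This MI is the only planned sensitivity analysis that fills in missing data, since the mFAS, CAS and PPAS repeats restrict the sample. An artificially wide interval could be read as fragility of the main result when it only reflects the imputation step.

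**Working it through.** **The plan's own figure.** With m = 10, Rubin's rules give 1 + 1/m = 1.1 and 1/(m − 1) = 1/9. Both match SAP 7.1.4, so the combining formula is correct. The SAP gives no other figure on this point.

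**Inputs.** From the documents: 10 imputations, baseline-adjusted ANCOVA, up to about 500 subjects. Assumed, because the documents are silent: 250 per arm, share p of missing baselines, baseline-outcome correlation ρ, baselines missing completely at random, and treatment group in the baseline imputation model.

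**Closed form.** Scale baseline and outcome to SD 1. If a share p of baselines is replaced by draws unrelated to the subject's outcome:

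- slope = (1 − p)ρ
- residual SD ratio = √{[1 − (1 − p)²ρ²] / (1 − ρ²)}

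For ρ = 0.9 and p = 0.05: √[(1 − 0.9025 × 0.81)/0.19] = √(0.2690/0.19) = 1.19.

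| ρ | p = 1% | 5% | 10% | 20% |
|---|---|---|---|---|
| 0.5 | 1.00 | 1.02 | 1.03 | 1.06 |
| 0.7 | 1.01 | 1.05 | 1.09 | 1.16 |
| 0.9 | 1.04 | 1.19 | 1.35 | 1.59 |

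This covers residual variance only. The between-imputation term 1.1B comes on top.

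**Simulation A: mJSW-like, no outcomes missing.** Baseline SD 1.2 mm, residual SD 0.5 mm and slope 1 give ρ = 1.2/√(1.2² + 0.5²) = 1.2/1.3 = 0.92. Mean standard error of the treatment difference (mm):

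| Missing baselines | SAP rule | Subjects dropped | Ratio |
|---|---|---|---|
| 1% | 0.048 | 0.045 | about 1.08 |
| 2% | 0.052 | 0.045 | about 1.15 |
| 5% | 0.061 | 0.046 | about 1.32 |
| 10% | 0.073 | 0.047 | 1.52-1.55 across runs |

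MI conditioning on the observed outcome equals the dropped-subjects column to three decimals. At ρ = 0.7 the ratio to dropping is 1.01, 1.04 and 1.07 at 1%, 5% and 10% missing. At ρ = 0.5 it is about 1.00 throughout (0.99 at 10%).

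**Simulation B: 10% of outcomes also missing, SD(outcome) = 1, 1,000 trials per row.**

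| ρ | Missing baselines | SAP rule | Conditional MI | Rise | Subjects dropped |
|---|---|---|---|---|---|
| 0.9 | 1% | 0.0434 | 0.0415 | 5% | 0.0414 |
| 0.9 | 5% | 0.0508 | 0.0423 | 20% | 0.0423 |
| 0.9 | 10% | 0.0585 | 0.0429 | 36% | 0.0434 |
| 0.5 | 5% | 0.0838 | 0.0825 | 2% | 0.0837 |
| 0.5 | 20% | 0.0883 | 0.0845 | 4% | 0.0915 |

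The rises at ρ = 0.9 are smaller than in A because the correlation is slightly lower and because some missing-baseline subjects have no real outcome to mismatch. The same point explains the slopes. With 90% of those subjects mismatched, the expected slope is 0.9(1 − 0.9p), or 0.86 at 5% and 0.82 at 10%. The simulation gave 0.859 and 0.819.

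**Direction of the error.** At ρ = 0.9, rejection under the null falls to 2.9%, 1.5% and 0.9% with 5%, 10% and 20% missing. At a true difference of 0.13 SD and 5% missing, power is 77% under the SAP rule, 89% with conditional MI and 88% with subjects dropped. With 10% missing, the actual spread of the estimate is 0.0488 against 0.0431 (up 13%), while the reported standard error is 0.0585 against 0.0429 (up 36%). Part of the inflation is therefore real and part is Rubin's formula overstating it. The estimate is unbiased when baselines are balanced. A 0.15 SD imbalance with 10% missing gives a bias of about 0.01 SD.

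**The case against.** The other side has four fair points, and most of each stands.

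- **Consequence.** The main analyses use available data in the FAS and are untouched. MI carries no decision rule. A reader might infer that the primary result or the type I error is at risk; the documents and the simulations do not support that, since the test becomes conservative.
- **Generality.** A reader might infer that the rule is always worse than dropping the affected subjects. That holds at high correlation. At ρ = 0.5 the two are about equal, and with 20% missing the rule is slightly better than dropping (0.0883 against 0.0915). It still trails conditional MI.
- **Exposure.** The documents give no count of missing baselines. Every subject had to complete and comply with the parent study (Protocol 5.1). Figure 1 of the protocol places the X-ray at parent Week 52, inside the permitted window, and some clinical assessments at Week 56. Pain NRS is collected at Visit 1E, with the injection as the last procedure (Protocol 7.3.4). Two of the seven OA-07-baseline hypotheses in SAP 9.2 therefore have a planned in-window value in this study. The other five (one mJSW, four WOMAC) rest on parent-study visits alone. The high-correlation figures suit mJSW and should not be read across to all seven.
- **Remedy.** Putting all later visits into the imputation model would bring in Visit 6E, after placebo subjects have crossed over to lorecivivint.

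None of this restores the rule. No other section corrects it. The SAP treats a missing baseline as possible: it writes a dedicated rule for it, and the CAS definition (SAP 6.5) explicitly requires a parent-study baseline.

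**Conclusion.** The point holds within limits. The prescribed step contradicts the section's own missing-at-random statement, attenuates the ANCOVA baseline slope and gives too large a standard error in the MI sensitivity analyses, with lost power.

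Its size rests on two assumed quantities, ρ and the share of missing baselines. At ρ near 0.9, which is plausible for repeated mJSW on one knee but not documented, it ranges from modest at 1% missing (5-8%) to large at 10% (36% in simulation B, 50-55% in A), and is then worse than dropping the subjects. At ρ = 0.5 with up to 10% missing it is 0-3% worse than conditional MI and no worse than dropping. If almost no baselines are missing, the effect is negligible. Exposure is most plausible for OA-07-baseline mJSW and WOMAC, and less so for Pain NRS. The documents give no specific reason to expect many missing parent-study baselines, on which the primary endpoint depends.

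**What to change.** Delete the blank-and-restore step from SAP 7.1.4 and choose one of two replacements:

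1. Exclude subjects without the relevant baseline from the MI. This is the simplest route. The available-data ANCOVA already omits them, because they have no change score.
2. Impute the missing baseline by fully conditional specification or MCMC from treatment group and the subject's observed blinded-period values (Visits 2E and 3E), leaving out post-crossover visits.

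In either case, report the number of missing baselines per arm, by outcome, for the parent-study and OA-07 baselines. If the counts are near zero, that table settles the matter.

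The cost is a sentence in the SAP and a small programming change, with no new data. The second option also departs slightly from the stated timepoint-by-timepoint imputation model, and the SAP should say so.
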